9.4 Serious and Unanticipated Adverse Device Effects

A serious and unanticipated adverse device effect is defined as "any serious adverse effect on health or safety or any life-threatening problem or death caused by, or associated with, a device

if that effect, problem, or death was not previously identified in nature, severity, or degree of incidence in the investigational plan, or any other unanticipated serious problem associated with a device that relates to the rights, safety or welfare of participants.”

9.5 Adverse Event Reporting

All AEs that occur during the course of the study should be reported on the Adverse Event CRF. The Investigator should determine the intensity of the event.

Mild	Awareness of sign or symptom, but easily tolerated
Moderate	Discomfort enough to cause interference with normal daily activities
Severe	Inability to perform normal daily activities

All SAEs and ADEs should be reported by the Investigator to [REDACTED] and the Sponsor in writing within 24 hours from the point in time when the Investigator becomes aware of the event. It is the responsibility of the Investigator to promptly notify the Institutional Review Board (IRB) of all unanticipated SAEs and unanticipated problems, per the IRBs reporting requirements.

Throughout the course of the proposed study, all efforts will be made to remain alert to possible adverse experiences or untoward findings. If adverse experiences occur, the first concern will be the safety and welfare of the participant. Appropriate medical intervention will be made.

[REDACTED] and the Sponsor will immediately conduct an evaluation of any UADE. The results of the evaluation will be reported to the IRB within 10 days of [REDACTED] and/or the Sponsor becoming aware of the event. If it is determined by [REDACTED] and the Sponsor to present an unreasonable risk to study participants, all investigations or parts of the investigation presenting that risk will be terminated as soon as possible. Termination will occur not later than five working days after [REDACTED] and the Sponsor makes this determination, and not later than 15 working days after first receiving notice of the event. [REDACTED] and the Sponsor will not resume an investigation terminated under these conditions without an additional IRB approval.

Contact information for reporting Serious Adverse Events:

[REDACTED]	[REDACTED]
------------	------------

Sponsor Contact Information	
[REDACTED]	[REDACTED]

Office [contact]
-------------------	--------------

9.6 Anticipated Adverse Events

The following is a list of potential AEs associated with the use of the device:

- Nasal discomfort or pain
- Epistaxis
- Excessive sneezing
- Nasal irritation, paresthesia or numbness post-stimulation
- Nasal infection, abrasion or inflammation
- Skin irritation or hypersensitivity
- Headache (e.g., tension, migraine, etc.)
- Facial pain
- Excessive salivation
- Sensation of teeth vibrating
- Excessive rhinorrhea
- Temporary aggravation of nasal allergies
- Allergic reaction to contact materials

The following is a list of potential AEs associated with the testing procedures at Screening or with CAE exposure:

- Ocular discomfort
- Moderate or severe conjunctival injection
- Clinically significant decrease in visual acuity
- Clinically significant increase in corneal or conjunctival epithelial defects
- With use of proparacaine, temporary burning, stinging and conjunctival redness of the eyes
- With use of proparacaine, a rare hyperallergic corneal reaction characterized by epithelial keratitis, sloughing of epithelium, corneal filaments and iritis
- With the Schirmer test, corneal irritation and abrasion
- Allergic reaction to contact materials

10.0 PREGNANCY

Women of Childbearing Potential (WOCBP) include any females who have experienced menarche and who have not undergone successful surgical sterilization (hysterectomy, bilateral tubal ligation or bilateral oophorectomy) or are not postmenopausal at least 12 months since last

menses. WOCBP will be required to use designated methods of birth control during the course of the study. All women who are pregnant, nursing an infant, or planning a pregnancy during the duration of this study will be excluded from participation.

If a participant or Investigator suspects that the participant may be pregnant prior to study device administration, the study device should be withheld until the results of pregnancy testing are available. If pregnancy is confirmed, the participant should not administer the study device and should not be enrolled in the study.

If a female participant becomes pregnant during the study, the Investigator will notify Allergan (or designee) immediately after the pregnancy is confirmed. The Investigator will (1) obtain a consent from the female participant for pregnancy follow-up and (2) follow the progress of the pregnancy to term. The Investigator should document the outcome of the pregnancy and provide a copy of the documentation to Allergan (or designee).

11.0 STATISTICAL HYPOTHESIS AND METHODS OF ANALYSES

11.1 Power Calculation and Determination of Sample Size

In a previous controlled study assessing the change in EDS while in the CAE at Day 0, the observed mean (SD) treatment difference for the TrueTear device compared to the control was -13.4 (23.9). It is unknown what, if any, effect on the change in EDS while in the CAE will be with the TrueTear device application after 45 days of use. Using an estimated standard deviation of 25, 45 participants will provide over 90% power to detect a EDS reduction of 13 based on a one-sided test at an α of 0.025.

In the previous study, approximately 10% of the participants did not reach the application threshold during the CAE session. In order to allow for participants that discontinue the study before Day 45 or do not reach the application threshold in the CAE, approximately 60 qualified participants will be identified to initiate the study to ensure Day 45 results for 45 participants.

11.2 Statistical Hypotheses and Level of Significance

The null hypothesis is, after 45 days of TrueTear use, neurostimulation fails to result in a statistically significant reduction in EDS exacerbated by exposure to the CAE.

The alternative hypothesis is, after 45 days of TrueTear use, neurostimulation will result in a statistically significant reduction in EDS exacerbated by exposure to the CAE.

The hypothesis can be expressed as:

$$H_0: \Delta \leq 0 \text{ mm}$$

$$H_A: \Delta > 0 \text{ mm}$$

where Δ represents the change in EDS score, symptom relief, from the TrueTear application. Statistical tests for the primary and exploratory effectiveness variables will be one-sided and evaluated at an α of 0.025.

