6.0 STUDY PARAMETERS

6.1 Effectiveness Measures

6.1.1 Primary Effectiveness Measure

The visual analog scale (VAS) has frequently been used for the collection of patient-reported outcomes and has been commonly used to assess dry eye symptoms in clinical studies.²⁰⁻²⁹ As such, the 2007 report of the International Dry Eye WorkShop (DEWS) listed the Visual Analog Scale as a well-defined symptom assessment methodology suitable for use in dry eye clinical trials.³⁰ Patient-reported outcomes assessed using the Eye Dryness Score (EDS) VAS have been used in other dry eye studies and were recently used as the primary symptom endpoint for FDA approval of lifitegrast (Xiidra®)

for the treatment of the signs and symptoms of dry eye disease.^{31,32,33} Based on this information, the EDS visual analog scale was selected as the primary effectiveness variable to provide a direct assessment of the participant’s perception of their current eye dryness symptoms.

The primary effectiveness measure will be the change in dry eye symptom severity score during CAE exposure at Study Day 45 assessed using the EDS. The EDS will be assessed using a self-administered VAS every five minutes during CAE exposure. The analysis variable will be the change in EDS values from the last time point prior to application administration to the subsequent time point following administration. The primary effectiveness analysis will compare the change in EDS between the pre-application and post-application scores to an expected change of 0. The test will be one-sided and evaluated at an α of 0.025 in the Full Analysis Set (FAS) population.

6.1.1 [REDACTED]

[REDACTED]

[REDACTED]

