11.8 Effectiveness Analyses

The primary effectiveness variable will be the change in EDS between the time point preceding application and the subsequent time point following application. The primary effectiveness endpoint will be the analysis of the primary effectiveness variable for the FAS population at Day

45 without imputation. The analysis will use a paired *t*-test or Wilcoxon signed-rank test, as appropriate, and will be evaluated at a one-sided α of 0.025. If $\geq 5\%$ of the FAS population is missing the primary effectiveness variable at Day 45, a sensitivity analysis of EDS difference at Day 45 will be performed by imputing the missing EDS difference as zero. Study participants with a missing Day 45 result will be imputed one at a time and the analysis will be repeated. This process will continue until either the result is no longer statistically significant or all participants with missing results have been imputed. As an additional sensitivity analysis, missing values will be imputed using a random selection process from the available Day 45 results and the analysis will be repeated. This process will be performed 10 times and a single combined p-value for the 10 imputations will be obtained by a method described in Rubin³⁸ and in the SAS manual for PROC MIANALYZE.³⁹ If the study includes more than one site, summaries of the primary effectiveness endpoint without imputation will be presented by site.

The primary effectiveness analysis will be repeated in the PP population as a sensitivity analysis.

The exploratory effectiveness variables will be the difference in EDS at Day 0, the difference in dry eye discomfort using the [REDACTED] Calibra scale in the FAS population at Day 0 and Day 45 and the difference in Schirmer test results at Day 7. The analysis will be performed using the same method as the primary effectiveness variable. Statistical significance will be determined using a one-sided test at an α of 0.025.

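### Does the one-sided EDS hypothesis in section 11.2 point in the wrong direction?

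*Combined protocol and SAP*

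**What the plan says.** Section 6.1.1 defines the analysis variable as the "change in EDS values from the last time point prior to application administration to the subsequent time point following administration" and compares it with an expected change of zero. It adds: "The test will be one-sided and evaluated at an α of 0.025 in the Full Analysis Set (FAS) population".

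Section 11.2 states the hypotheses twice. In words, the alternative is that stimulation after 45 days of use reduces EDS. In symbols, H0 is Δ ≤ 0 mm and HA is Δ > 0 mm, where Δ "represents the change in EDS score, symptom relief, from the TrueTear application". It then extends the rule: "Statistical tests for the primary and exploratory effectiveness variables will be one-sided and evaluated at an α of 0.025".

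The synopsis equates acute symptom relief at Day 45 with the difference between the two readings and names the pre-application reading first. Section 11.1 reports an earlier device-versus-control difference of -13.4 (SD 23.9) and bases the sample size on the statement that "45 participants will provide over 90% power to detect a EDS reduction of 13". Section 11.8 specifies a paired t-test or Wilcoxon signed-rank test. For the exploratory variables, which include the Day 7 Schirmer difference, it says: "The analysis will be performed using the same method as the primary effectiveness variable".

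**The concern.** In a one-sided test the sign of the difference is the decision rule. A change from one time point to the next is normally the later value minus the earlier one. Appendix 2 anchors the EDS at 0 for none and 100 for maximal, so a working device would give a negative change under section 6.1.1. The -13.4 in section 11.1 appears to follow the same convention. Taking Δ as that change and rejecting only for Δ > 0 would fail an effective device and could pass one that makes dryness worse.

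The Schirmer test seems to compound this. Benefit there is an increase in wetting, so a single subtraction order carried across both variables would put one of them in the wrong tail. The verbal hypotheses also refer to statistical significance, which is a result of a test and not a property of a parameter.

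**Working it through.** **Inputs.** Mean reduction 13, SD 25, n = 45 (section 11.1); one-sided α = 0.025 (sections 6.1.1, 11.2 and 11.8); lower EDS is better (Appendix 2, EDS VAS).

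**Step 1: reproduce the stated power.**
- Standard error = 25/√45 = 3.727.
- Noncentrality = 13/3.727 = 3.488.
- Critical value of t on 44 degrees of freedom = 2.015.
- Exact power, P(T > 2.015) with noncentrality 3.488: **92.7%**.
- Normal approximation, Φ(3.488 − 1.960) = Φ(1.528): 93.7%.

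Both agree with the plan's figure of over 90%.

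**Step 2: the same calculation under each reading of Δ.**

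| Reading | True mean Δ | Rejects for | Power | One-sided p if the observed mean fall is 13 with SD 25 |
|---|---|---|---|---|
| Δ = pre − post (relief) | +13 | Δ > 0 | 92.7% | 0.0006 |
| Δ = post − pre, tail for a reduction | −13 | Δ < 0 | 92.7% | 0.0006 |
| Δ = post − pre, symbols taken literally | −13 | Δ > 0 | about 4 × 10⁻⁸ | 0.9994 |

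The first two rows are the same test. Only the third is damaging, and it contradicts section 11.1: a plan that counted only an increase as success could not claim over 90% power to detect a reduction.

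**Step 3: set the statements of direction side by side.**

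| Place | What it implies |
|---|---|
| Section 3.0, clinical hypothesis | Success is a reduction |
| Section 11.2, hypotheses in words | Success is a reduction |
| Section 11.2, label on Δ | Relief, so positive is good |
| Synopsis, definition of relief | Pre-application listed first; consistent with positive is good |
| Section 11.1, effect size | Reduction given as a positive 13 |
| Section 6.1.1, analysis variable | From-to wording; suggests post − pre, subtraction not written |
| Section 11.8, analysis variable | Change between two time points; no direction |
| Section 11.1, earlier study | −13.4, but a between-group difference from another trial |

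Every statement about what counts as success points the same way. The only tension is with the word change, and chiefly with the phrasing of section 6.1.1.

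**Step 4: Schirmer.** The sentence on method in section 11.8 follows a description of a paired t-test or signed-rank test at one-sided 0.025. It carries over the test and the level. It need not carry over the order of subtraction, and the Δ hypotheses in section 11.2 are written for EDS only. Sections 1.3 and 7.0 present the device as a means of increasing tear production, so the direction for Schirmer is not in doubt.

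**The case for a change.** The strongest counter-argument is that the direction of a one-sided primary test should be legible from its formal definition. Here Δ carries two labels that have opposite signs under section 6.1.1, and no passage gives the subtraction. The synopsis does not settle it alone, since listing the pre-application value first is a convention just as the from-to phrasing is. Even a reader who settles on pre minus post for EDS could carry that order to Schirmer and test the wrong tail. One sentence would remove all of this at no cost.

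The textual point stands: the notation is careless. The consequence does not follow. The direction is fixed before any data are seen, because sections 3.0 and 11.2 both state it as a reduction, so there is no freedom to choose the tail afterwards. A programming slip would also be conspicuous, since the wrong-tail p is one minus the right-tail p: a clear fall in EDS would be reported beside p = 0.9994. For Schirmer the variable is exploratory, and much of the text on exploratory measures and on the Visit 3 procedures is redacted, so a missing definition cannot be inferred. The significance wording is a matter of style, because parameter statements follow it directly in the same section.

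**Conclusion.** The hypothesis is not shown to have the wrong sign. Read with its own label of relief and its own verbal alternative, Δ > 0 is the direction of benefit, and the test has 92.7% power for the planned effect at one-sided 0.025 with 45 participants. The p-value of 0.9994 and the near-zero power arise only if a reader ignores the label, both verbal hypotheses and the power statement.

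What remains is an unwritten subtraction that an analyst would supply correctly: pre minus post for EDS, or equivalently post minus pre with the lower tail, and an increase as benefit for Schirmer. Writing it down would be tidy, but would alter no estimate, p-value, sample size or conclusion. No change to the plan is called for. The conclusion assumes that the analyst follows the stated direction of benefit; the power figure also rests on the plan's assumed SD of 25 and a paired t-test.

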11.3 Randomization

This study is not randomized.

11.4 Evaluability of Data

All participants who initiated at least one study application will be eligible for inclusion in the analyses. Participation in the study will be summarized by presenting the number of participants who were enrolled, the number of participants who completed the study, and the number of participants who did not complete the study due to not reaching the threshold or by reason of early discontinuation.

Full Analysis Set Population (FAS): The FAS population will include all participants who initiated at least one application of the TrueTear device at any point during the study.

Per protocol population (PP): The PP population is a subset of the FAS population, which did not have a major protocol deviation likely to seriously affect the primary outcome of the study. This population will be the secondary population for the effectiveness analyses and will also be used to summarize the primary and exploratory effectiveness variables. If the PP and FAS populations are exactly the same, then additional efficacy analyses on the PP population will not be performed.

Safety Population: The safety population will be the same as the FAS population.

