9.0 ADVERSE EVENTS

An AE is defined as any unfavorable and unintended sign (including an abnormal laboratory finding) symptom, or disease temporally associated with the use of an investigational product but not necessarily related to the investigational product. An AE may also be called a complication. The capture of AEs will begin with the participant's entry into the CAE.

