11.9 Safety Analyses

The safety analyses will be performed for the Safety population. The primary safety endpoint will be the proportion of participants who experience one or more device-related AEs for each application and overall. The proportion and exact 95% confidence interval will be computed. Any changes in corrected distance visual acuity or slit lamp biomicroscopy findings will be summarized.

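### Participants who enter the Day 0 CAE but never apply TrueTear have AEs captured, yet fall outside the Safety population and its summaries

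*Combined protocol and SAP*

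**What the plan says.** All references are to the combined protocol and SAP.

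- **Population.** Section 11.4: "Safety Population: The safety population will be the same as the FAS population". On the FAS it says: "The FAS population will include all participants who initiated at least one application of the TrueTear device at any point during the study". The same section opens with a general rule: "All participants who initiated at least one study application will be eligible for inclusion in the analyses".
- **Use of the population.** Section 11.9: "The safety analyses will be performed for the Safety population". It then names the main output: "The primary safety endpoint will be the proportion of participants who experience one or more device-related AEs for each application and overall". An exact 95% confidence interval is attached to that proportion. Changes in corrected distance visual acuity and slit-lamp findings are to be summarised as well.
- **Start of AE capture.** Section 9.0: "The capture of AEs will begin with the participant's entry into the CAE".
- **Risks of the CAE itself.** Section 9.6 has a list separate from the device list, introduced by "The following is a list of potential AEs associated with the testing procedures at Screening or with CAE exposure". It includes ocular discomfort, conjunctival injection, loss of acuity and epithelial defects.
- **AEs without device exposure.** The relationship scale in 9.3 has a Not applicable grade for participants not exposed to the device.
- **Threshold.** Section 11.1 reports that in the previous study "approximately 10% of the participants did not reach the application threshold during the CAE session". Section 11.4 counts failure to reach the threshold among the reasons for not completing the study.

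**The concern.** CAE exposure is a study procedure with its own listed risks, and the plan collects AEs from the moment it begins. Membership of the Safety population depends on something that happens later, namely whether the participant initiates an application. For most participants this makes no difference. For someone who enters the CAE and never applies the device, the data are collected and then have no place in the analysis.

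The exclusion need not be random. A participant who leaves the CAE because of an ocular AE before applying the device is excluded as a consequence of that AE. This is also the participant who says most about how well the CAE is tolerated. What is at stake is the completeness of the descriptive safety account of the CAE: the acuity and slit-lamp summaries, and any summary of AEs that are not device-related.

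**Working it through.** **Order of events on Day 0**

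1. Home devices are dispensed after training and before CAE entry (8.2).
2. TrueTear is not to be used earlier on the day of Visit 2; application takes place in the CAE, and further use is allowed afterwards (8.1.3).
3. The participant enters the CAE and AE capture starts (9.0).
4. The first stimulation is given during that session (8.2), if the application threshold is reached (11.1).

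Every participant therefore has a period of CAE exposure and AE capture before any device exposure.

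**Who falls outside the Safety population**

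| Course after Day 0 CAE entry | AEs captured (9.0) | In Safety population (11.4) |
|---|---|---|
| Applies the device in the CAE | Yes | Yes |
| Misses the threshold, later uses the device at home | Yes | Yes |
| Misses the threshold, never applies the device | Yes | No |
| Leaves the CAE before applying, never applies the device | Yes | No |

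Only the last two rows are affected.

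**Head count**

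Inputs: about 60 enrolled, 45 required at Day 45, and 10% not reaching the threshold (all from 11.1).

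- The plan's own allowance is 60 − 45 = 15 participants, or 15/60 = 25%, for discontinuation and missed thresholds together.
- Expected to miss the threshold on Day 0 at the 10% rate: 60 × 0.10 = 6.
- If all 6 later use the device at home, 0 are excluded. If none does, about 6 are excluded and the Safety population is about 60 − 6 = 54. Early exits are additional, and the documents give no rate for them.
- Upper end at other assumed rates: 5% gives 3, 15% gives 9, 20% gives 12.
- Chance that at least one of 60 misses the threshold at 10%: 1 − 0.9^60 = 99.8%. This is the chance of a missed threshold, not of an exclusion.

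**Chance that an AE goes unsummarised**

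The documents give no rate for CAE-related AEs, so the risk q per participant is an assumption. At the upper end of 6 excluded participants, the chance that at least one has such an AE is 1 − (1 − q)^6:

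- q = 5%: 1 − 0.95^6 = 26%
- q = 10%: 1 − 0.90^6 = 47%
- q = 20%: 1 − 0.80^6 = 74%

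With fewer excluded, these fall, and with none excluded they are zero.

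**Effect on the planned outputs in 11.9**

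- Device-related AE proportion: unchanged. A participant never exposed to the device cannot have a device-related AE and does not belong in that denominator.
- Acuity and slit-lamp summaries: participants without any application are missing.
- AEs not related to the device: the visible text specifies no table of these for anyone, so widening the population alone would not produce one.

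**The case against.** The case for leaving the plan as it is has several parts, and most of them limit the point.

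- **Missing the Day 0 threshold does not by itself exclude anyone.** A reader might infer that all non-reachers drop out of the safety analysis. The documents do not support that. The FAS accepts an application at any point in the study, and devices for home use are already in participants' hands. Section 11.4 does not say at which CAE visit a missed threshold ends participation, and the visit procedures in 8.4 are largely redacted. This stands, and is why the lower end of the range is 0.
- **The planned safety rate is not biased.** A reader might infer that a reported AE proportion is understated. The only safety proportion in the visible plan is for device-related AEs, and an application-based set is the right denominator for it. The plan computes no proportion for CAE-related AEs, so no such figure can be said to be wrong. This stands in full.
- **Nothing is lost from safety reporting.** All AEs go on the CRF and SAEs are reported within 24 hours (9.5). Early discontinuations are documented with reasons (5.6), withdrawals are tabulated by reason (11.6), and missed thresholds are counted (11.4). This also stands: the gap is in analysis. A withdrawal table gives a reason for leaving, however, and does not summarise AEs, acuity or slit-lamp findings.
- **Redaction.** The safety measures in 6.2 and the safety entries in the synopsis are blacked out, so a listing for all CAE entrants could be there. This cannot be excluded. But 11.9 is readable, ties the safety analyses to the Safety population, and provides no such listing.
- **The CAE is a test model and not the product under study.** True, but the protocol lists its risks and starts AE capture with it.

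**Conclusion.** The point holds in a limited form. Participants who enter the Day 0 CAE and never initiate any application have AEs captured under 9.0, but 11.4 puts them outside the Safety population. They are therefore absent from the acuity and slit-lamp summaries in 11.9 and from any AE summary. The number is 0 to about 6 of 60, plus any early exits from the CAE. It rests on the previous study's 10% rate applying here, and on how many non-reachers go on to home use, which the visible text does not settle.

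The primary effectiveness analysis, the FAS and the device-related AE proportion are untouched. This is an inexpensive improvement to descriptive safety reporting and does not call the main conclusions into question.

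**What to change.** 1. In 11.4, define the Safety population as all participants who entered the CAE at Day 0, or keep the present definition and add a CAE-exposed safety set with that entry condition.
2. In 11.9, summarise all AEs on that set, including those attributed to the CAE or to study procedures, together with acuity and slit-lamp changes. This sentence is needed as well as the first, because a wider population without a planned AE table would still leave these AEs unsummarised.
3. In 11.9, keep participants with at least one application as the denominator for the device-related AE proportion, so that participants who were not exposed do not dilute it.
4. Report how many CAE entrants never initiated an application, so that the size of the group is visible.

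The FAS stays as it is. The cost is a few sentences in two sections, one extra denominator and a descriptive table. AEs from CAE entry are already on the CRF, and safety evaluations are already requested, with the participant's agreement, at early termination (5.6 and the early termination section of 8.4). No new data collection is needed.
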